### 10.2.2 Injection site reaction

Injection site reactions are recorded at the AE CRF page at the time when they occur. All AEs will be coded and classified by system organ class, high level term, and preferred term. An AE with High Level Terms of "Administration site reactions NEC" and "Injection site reactions" will be evaluated as injection site reaction.

All injection site reactions for self-injection with a start date on or following the first self-administration of study treatment through the final self-administration of study treatment + 7 days will be listed.

### **10.3 Clinical laboratory evaluations**

All clinical laboratory evaluations including hematology, chemistry and urinalysis will be collected in PS0014.

### **10.4 Vital signs, physical findings, and other observations related to safety**

eCRF data of vital signs, Electrocardiograms, physical examination and pregnancy test results will be collected in PS0014.

## **11 OTHER ANALYSES**

This section contains a detailed description of the analysis of the primary, secondary and other outcome variables. All statistical analyses will be descriptive in nature. No inferential statistical analyses are planned. The analysis is done on FAS-s and FAS-a, respectively.

### **11.1 Primary outcome**

The primary outcome variable is the percentage of all subjects able to self-administer safe and effective injections using the given device at DV0002 Week 8. Safe and effective self-injection will be evaluated by the study personnel as defined below:

- Complete dose delivery: Subject self-injects the complete dose of bimekizumab as confirmed by a visual inspection of the investigational device which shows that the IMP is delivered completely (ie, container is empty), and
- No ADEs that would preclude continued use of the device for self-injection (ie, no SADEs and/or ADEs leading to withdrawal from the DV0002 substudy).

All data to assess the primary outcome is collected on the subject self-injection of bimekizumab CRF page for DV0002 Week 8. For the number of subjects with safe and effective self-injections simply the cases which indicated “yes” for the question “Did the subject self-inject the complete dose of Bimekizumab” and “no” for the question “Where there any AEs related to use of the investigational device for self-injection” at Week 8 are counted.

For subjects in the 1mL device cohort, two self-injections will be performed at DV0002 Week 8 and the questions will be answered twice. If the answers are different between both self-injections in one visit, then the worst case of both answers will be used for analysis at this visit. Subjects with only one self-injection at one visit will be counted as non-responder. Assessments where the self-injection was not performed by the subject will be not included in any summary statistics.

The number and percentage of subjects with safe and effective self-injections will be tabulated separately for each device overall and within each device by dosing regimen. The 90% CIs based on the Exact Binomial method will be reported as well.

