4 STUDY VARIABLES

4.1 Outcome variables

4.1.1 Primary outcome variable

The primary outcome variable is the percentage of subjects able to self-administer safe and effective injections using the bimekizumab-SS-1mL, bimekizumab-AI-1mL, bimekizumab-SS-2mL, or bimekizumab-AI-2mL, 8 weeks after training in self-injection technique. Safe and effective self-injection will be evaluated by the study personnel and is defined as:

- Complete dose delivery: Subject self-injects the complete dose of bimekizumab as confirmed by a visual inspection of the device which shows that the IMP is delivered completely (ie, container is empty), and
- No ADEs that would preclude continued use of the device for self-injection (ie, no SADEs and/or ADEs leading to withdrawal from the DV0002 substudy).

In the DV0002 substudy, for the 1mL devices, the 320mg bimekizumab dose will be administered as two 160mg injections with either 2 bimekizumab-SS-1mL devices or 2 bimekizumab-AI-1mL devices. Each self-injection will be evaluated for safety and effectiveness by study personnel using the above criteria. The endpoint of safe and effective self-injection will be met only if both self-injections are determined to be safe and effective.

For the 2mL devices, the 320mg bimekizumab dose will be administered as 1 injection with either 1 bimekizumab-SS-2mL or 1 bimekizumab-AI-2mL device. Each self-injection will be evaluated for safety and effectiveness by study personnel using the above criteria. The endpoint of safe and effective self-injection will be met if the single self-injection is determined to be safe and effective.

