7.2 Treatment to be administered

The IMP used in this study is bimekizumab. Bimekizumab will be supplied at a concentration of 160mg/mL (55mM sodium acetate, 220mM glycine, 0.04% polysorbate 80 at pH 5.0) for sc injection.

1mL Device Cohort

For the 1mL device cohort, IMP will be supplied in 2 investigational devices: bimekizumab-SS-1mL or the bimekizumab-AI-1mL.

The IMP will be administered according to the schedule shown in [Table 5-1](#). Subjects will be assigned to the use of 1 device and will receive the following doses of IMP based on their established dosing regimen in PS0014:

- 320mg bimekizumab, Q8W or

- 320mg bimekizumab, Q4W.

Regardless of the assigned dose regimen, subjects will perform self-injection with the assigned device only at Baseline and at Week 8. For the 1mL device cohort, the 320mg bimekizumab dose will be administered as two 160mg injections with either 2 bimekizumab-SS-1mL or 2 bimekizumab-AI-1mL devices. At all visits except Baseline and Week 8, the 320mg bimekizumab dose will be administered as two 160mg injections in a 1mL PFS by study personnel (ie, the same administration manner and device used in PS0014).

The investigational devices will be used as described in the IFU. Subjects will be observed onsite for 30 minutes after self-injection with bimekizumab for any AEs. Subjects will be asked to contact the designated site personnel in case any AEs occur outside of the site visits. Of note, reported AEs related to IMP will be assessed within PS0014 and reported ADEs and device deficiencies will be assessed within DV0002.

2mL Device Cohort

For the 2mL device Cohort, IMP will be supplied in 2 investigational devices: bimekizumab-SS-2mL or bimekizumab-AI-2mL.

The IMP will be administered according to the schedule shown in [Table 5-2](#). Subjects will be assigned to the use of 1 device and will receive the following doses of IMP based on their dosing regimen in PS0014:

- 320mg bimekizumab, Q8W or
- 320mg bimekizumab, Q4W.

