8.1.4 Visit 3a (Week 9; safety follow-up telephone call)

Visit 3a (Week 9) will occur in the DV0002 substudy, but not in the PS0014 study. The following procedures/assessments will be performed:

- Concomitant medication (DV0002-specific).
- Recording of AEs and ADEs (DV0002-specific).

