### 10.2.1 Adverse device effects

Adverse events are recorded at the AE CRF page at the time when they occur. If an adverse event is related to the device by assessment of the investigator it is counted as an Adverse device event. For DV0002 only ADE will be considered which started during the DV0002 study period. And ADEs started in the 1 ml phase will be included for 1 ml phase analysis, and those started in the 2 ml phase will be included for the 2 ml phase analysis. For 2 ml phase analysis, adverse device effects include those that started on or before the later of the final contact date or (the last injection date + 7 days).

All ADE data will be listed and no statistical testing will be performed. Only treatment-emergent ADEs will be included in the summary tables. Treatment-emergent ADEs (TEADEs) will be defined as events that have a start date on or following the first self-administration of study treatment in DV0002 through the final self-administration of study treatment + 7 days. The device SFU will occur 1 week after the last self-administration.

All ADEs will be coded and classified by system organ class, high level term, and preferred term. Adverse device effects will be summarized by the frequency and percentage of subjects having 1 or more of the events in question. Additional planned summaries include overall ADEs and SADEs. All summaries are presented by PS0014 treatment

- Incidence of TEADEs – Overview
- Incidence of TEADEs by SOC, HLT, and PT
- Incidence of serious TEADEs by SOC, HLT, and PT
- Incidence of TEADEs leading to death
- Incidence of TEADEs leading to discontinuation
- Incidence of non-TEADEs (only listed and not summarized in a table)

For definition of serious, unanticipated and serious unanticipated ADEs see protocol of DV0002.

Adverse device effects which started before DV0002 Week 16 and were ongoing at the data cut off will be included with the status remaining as ongoing. Adverse device effects which were ongoing at DV0002 Week 16 but with an end date before the data cut off will be included with their end date as recorded.

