## 11.2 Secondary outcome

The secondary outcome variable is the percentage of subjects able to self-administer safe and effective injections using the given device at DV0002 Baseline (first self-injection visit). Safe and effective self-injection will be evaluated by the study personnel. The secondary outcome variables will be analyzed in the same manner as the primary outcome variable.

All data to assess the secondary outcome is collected on Subject self-injection of Bimekizumab CRF page for DV0002 Baseline.

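### The safety half of the primary and secondary endpoints is scored only from the visit's self-injection CRF page, and nothing requires a later serious or withdrawal-causing ADE to count

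*SAP*

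**What the plan says.** Protocol 4.1.1, repeated in SAP 2.2.1 and 11.1, makes a self-injection safe and effective if the dose is completely delivered and a safety condition holds: "No ADEs that would preclude continued use of the device for self-injection (ie, no SADEs and/or ADEs leading to withdrawal from the DV0002 substudy". No time limit is attached to that condition.

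The scoring rule is in SAP 11.1: "All data to assess the primary outcome is collected on the subject self-injection of bimekizumab CRF page for DV0002 Week 8". A subject succeeds if the page says yes to complete dose and no to the item "Where there any AEs related to use of the investigational device for self-injection" (SAP spelling). For the secondary endpoint, SAP 11.2 states: "All data to assess the secondary outcome is collected on Subject self-injection of Bimekizumab CRF page for DV0002 Baseline".

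ADEs have their own route. SAP 10.2.1 says "Adverse events are recorded at the AE CRF page at the time when they occur", and counts an ADE as treatment-emergent from the first self-injection "through the final self-administration of study treatment + 7 days". Under Protocol 7.2, "Subjects will be observed onsite for 30 minutes after self-injection with bimekizumab for any AEs", and subjects are asked to contact the site about AEs arising between visits. A telephone call at Week 9 collects further AEs (Protocol 8.1.4 and 8.2.4; SAP 2.3.3).

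**The concern.** The endpoint is defined by two kinds of event, and neither is confined to the visit. A serious device effect may begin days after the injection. Withdrawal from the substudy is a decision that will usually be taken later. The SAP scores the endpoint from a visit page whose safety item, as quoted, asks about neither seriousness nor withdrawal. The data that hold this information (AE page, Week 9 call, discontinuation reason) are collected but are not named as inputs.

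At stake is whether the reported safe-and-effective percentage measures what Protocol 4.1.1 says it measures. An event could be tabulated as a serious TEADE, or as one leading to discontinuation, while the injection that caused it counts as safe in the same report.

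**Working it through.** **Step 1: definition against scoring rule.**

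| Element | Definition (Protocol 4.1.1) | Scoring (SAP 11.1, 11.2) |
|---|---|---|
| Which ADEs fail | Serious, or leading to DV0002 withdrawal | Any device-related AE |
| When | No limit stated | As answered on the Week 8 or Baseline page |
| Source | Not stated | Self-injection page only |

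The two differ in which events count and in which events are captured. SAP 3.10, which lists changes from the protocol's analyses, mentions neither difference.

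**Step 2: two hypothetical subjects, pages left uncorrected.**

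- Complete dose at Week 8, nothing noted at the visit, a SADE starting three days later. This is a failure by definition and a primary success as scored. The event falls inside the +7-day TEADE window, so it is also tabulated as serious.
- Complete dose at Baseline, nothing noted, an ADE on Day 4 that leads to withdrawal. This is a failure by definition and a secondary success as scored. The subject also has no Week 8 assessment and, under the observed-data denominator in SAP 3.1, leaves the primary percentage.

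**Step 3: size for late events alone.** The plan gives no figure to reproduce. Inputs are about 100 subjects per 1mL arm and about 50 per 2mL arm (SAP 2.3.6), and exact binomial 90% intervals (SAP 11.1). The number of late qualifying events is an assumption, 0 to 3 per arm, with every other subject a success.

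One missed event changes the percentage by 1/100 = 1 point or 1/50 = 2 points. With x successes out of n, the exact lower limit is the 5% quantile of Beta(x, n − x + 1), which is 0.05^(1/n) when x = n. The upper limit is the 95% quantile of Beta(x + 1, n − x), or 100% when x = n.

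| Late events | n = 100: % (90% CI) | n = 50: % (90% CI) |
|---|---|---|
| 0 | 100 (97.0–100) | 100 (94.2–100) |
| 1 | 99.0 (95.3–99.9) | 98.0 (90.9–99.9) |
| 2 | 98.0 (93.8–99.6) | 96.0 (87.9–99.3) |
| 3 | 97.0 (92.4–99.2) | 94.0 (85.2–98.3) |

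With uncorrected pages, the SAP rule would report the top row in every case. The first missed event raises the lower limit by 97.0 − 95.3 = 1.7 points, or 94.2 − 90.9 = 3.3 points.

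The chance of at least one such event is 1 − (1 − p)^n. For assumed true rates p of 0.5%, 1%, 2% and 5%, this is 39%, 63%, 87% and 99% at n = 100, and 22%, 40%, 64% and 92% at n = 50. The documents give no rate, so none of these values of p is favoured.

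**Step 4: the opposing error.** Let L be the subjects whose late qualifying ADE is missed, and M the subjects who fail on the page only because of a minor device-related AE known at the visit. The scored percentage minus the defined percentage is (L − M)/n. With L = 1, M = 0 and n = 100 it is +1 point; with L = 1 and M = 2 it is −1 point. Neither L nor M is given.

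**The case against.** The strongest reply is that the self-injection page need not be frozen at the visit. Naming it the Week 8 page says which visit it belongs to, not when it closes. The quoted item has no time limit, and the 30-minute observation is not tied to completing it. Protocol 13.3.1 allows corrections with a reason and leaves detail to completion guidelines that are not among the documents. Protocol 13.3.2 plans computerised and manual discrepancy checks, which might query a device-related AE entered against a no on the page. This stands to the extent that late events may be picked up. It does not close the gap, because nothing in the documents requires a correction or names such a check.

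The reply can add that study personnel evaluate each self-injection, and that Tables 5-3 and 5-5 schedule the evaluation only at Baseline and Week 8. An at-visit reading is therefore possible, but a criterion based on withdrawal from the substudy fits it poorly.

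A reader might infer more than the text supports:

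- That the endpoint cannot register late events. This would need the page to close at the visit, which no section says.
- That the percentages are biased upwards overall, or mostly measure dose delivery. Step 4 shows why the net sign is unknown: for events known at the visit, the CRF item is stricter than the definition.
- That the TEADE tables would contradict the endpoint. A different window and source can give a different answer without contradiction, and late events remain visible in the tables and listings.

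**Conclusion.** The concern holds in a limited form. SAP 11.1 and 11.2 do not implement the safety component that Protocol 4.1.1 defines, and whether a late qualifying ADE counts is left to site practice. For late events alone the error can only overstate success, by 1 point per event at about 100 subjects and 2 points at about 50. These sizes assume uncorrected pages and an event count that the documents do not supply and that may be zero. The net direction is unknown.

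This is a specification gap in the primary endpoint that should be corrected, not a demonstrated error in its result. The study is estimation only, with no hypothesis test or success threshold (Protocol 14.2; SAP 2.4 and 11), so no pass/fail decision turns on a shift of this size, and late ADEs are still reported as safety data.

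**What to change.** In SAP 11.1 and 11.2:

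- Take dose delivery from the self-injection page.
- Derive the safety component from the AE page: device-related, and serious or leading to withdrawal from DV0002. This replaces the any-AE item for scoring, so that the score matches the definition.
- Attribute each event to the preceding self-injection visit if it starts within one prespecified window, the same for Baseline and Week 8. The +7 days already used for TEADEs is a natural choice. Running the Baseline window to the next self-injection would give it about 8 weeks against about 7 days for Week 8, and the two percentages would not be comparable.
- State that a withdrawal decided after the window still counts if the ADE causing it started within it.
- Reconcile the AE page with the self-injection page.

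The cost is SAP wording and one extra merge of data already collected. Protocol 11.1.2.1 already has the eCRF record device relationship and the device concerned. The reported percentages may change slightly, in either direction. The change does not settle how subjects with no Week 8 assessment enter the primary denominator.

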3 STUDY OBJECTIVES

3.1 Primary objective

The primary objective of the study is to evaluate, for each device, the ability of subjects with moderate to severe chronic plaque PSO to safely and effectively self-inject bimekizumab 8 weeks after training in the self-injection technique.

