7.6 Drug and device accountability

The Investigator will receive numbered treatments that will be assigned to eligible subjects by an IRT at Baseline. All IMP administrations will be observed by the Investigator or his/her appropriately trained designee.

Appropriate accountability forms that reflect the receipt and use of the IMP and the investigational devices will be supplied to the investigational site. Details of any loss of the self-injection investigational devices due to breakage or wastage, non-use, destruction at the study site, or return to the Sponsor or designee must also be recorded on these forms. All supplies and pharmacy documentation must be made available throughout the study for UCB (or designee) to review.

The Investigator (or designee) is responsible for retaining all used, unused, and partially used IMP and investigational devices until returned to UCB. Used or partially used devices are to be stored at room temperature in a secured area and may only be destroyed following UCB's instruction. Devices with noted deficiencies are to be returned to UCB immediately. The Investigator may assign some of the Investigator's duties for drug accountability at the study site to an appropriate pharmacist/designee.

The IMP and investigational devices intended for the study cannot be used for any other purpose than that described in this protocol.

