7.7 Procedures for monitoring subject compliance

During the Treatment Period of this study, IMP administration (either self-administration or study personnel-administration) will be performed in the clinic and observed by the Investigator or his/her designee. Subject compliance will be reported in the PS0014 study.

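### Week 8 success is scored without asking about help: prompted injections count as successes, partial physical help is left undefined, and takeovers leave the statistics instead of counting as failures

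*SAP*

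**What the plan says.** Protocol 3.1 sets the aim as the ability to "safely and effectively self-inject bimekizumab 8 weeks after training in the self-injection technique". The schedules of assessments (Protocol Tables 5-3 and 5-5) place self-injection training at Visit 1 only. The secondary outcome measures performance straight after that training, and the primary outcome measures it 8 weeks later.

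Protocol 4.1.1 defines success by two components. The first is "Complete dose delivery: Subject self-injects the complete dose of bimekizumab as confirmed by a visual inspection of the device", the second the absence of an adverse device effect that would rule out further use. Study personnel make the evaluation. SAP 11.1 turns this into a count from one CRF page: "For the number of subjects with safe and effective self-injections simply the cases which indicated" a yes to "Did the subject self-inject the complete dose of Bimekizumab" and a no to "Where there any AEs related to use of the investigational device for self-injection". (The SAP's AE question is wider than the Protocol's second component; that is a separate matter.)

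On staff presence, Protocol 7.6 states "All IMP administrations will be observed by the Investigator or his/her appropriately trained designee", and Protocol 7.7 says that administration "will be performed in the clinic and observed by the Investigator or his/her designee".

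On injections given by someone else, SAP 11.1 has one rule: "Assessments where the self-injection was not performed by the subject will be not included in any summary statistics". SAP 11.3 repeats it for the other outcomes, and SAP 9.1 likewise keeps PK samples out of the summaries when site personnel or a caregiver gave an injection meant to be self-administered. SAP 3.1 bases outcome percentages on subjects with observed data, so an excluded assessment also leaves the denominator.

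**The concern.** The Week 8 result differs in meaning from the Baseline result only if the subject is not coached again at Week 8. Neither document says this. The people watching are also the people scoring, and the two counted answers do not separate a subject who remembered the steps from one who was reminded of them.

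The SAP's authors foresaw that someone other than the subject might be involved. They dealt with the complete takeover and left everything short of it undefined. Even the takeover rule removes the assessment and does not score it as a failure, so a subject who could not manage the injection disappears from the estimate.

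At stake is what the primary percentage can be said to show: independent ability after 8 weeks, or performance with trained staff at hand. Protocol 5.4 expects most commercial users to self-inject, which makes the first the quantity of interest. Entry also requires the subject to be willing and judged able to use the device (Protocol 6.1). Failures may therefore be few, and a handful of reclassified subjects would be a large share of them.

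**Working it through.** **Inputs.** Arm sizes are about 200/2 = 100 per device in the 1mL cohort and 100/2 = 50 in the 2mL cohort (Protocol 5.1.2). The interval is the exact binomial 90% CI (SAP 11.1). The plan gives no expected success rate, threshold or power, so there is no figure of its own to reproduce. The number of subjects helped, h, is an assumption, shown from 0 to 10 per arm.

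**Step 1: what the rules do with each kind of help at Week 8.**

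| Event | Outcome under the written rules |
|---|---|
| Verbal prompting, container empty, no device-related AE | Both CRF answers are met: success |
| Partial physical help | Not defined. The site could answer yes, answer no, or treat the injection as not performed by the subject |
| Takeover by staff or caregiver | Excluded from all summaries |

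The 1mL cohort has a further ambiguity. SAP 11.1 counts a subject with only one self-injection at a visit as a non-responder. If one of the two injections is taken over, that sentence and the exclusion sentence both apply, and the SAP does not say which prevails.

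**Step 2: size per subject, against counting the subject as not successful.** Let s be the number of unaided successes.

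- Helped subjects scored as success: (s + h)/n − s/n = h/n. One subject moves the estimate by 1/100 = 1 point or 1/50 = 2 points.
- Taken-over subjects excluded: s/(n − h) − s/n = [s/(n − h)] × (h/n). This is at most h/n, and equals it when everyone else succeeds.
- Partial help judged a failure by the site: no shift.

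No entry is negative, so the direction is upward or nil.

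**Step 3: exact 90% intervals.** The lower limit is the 5th percentile of Beta(x, n − x + 1) and the upper limit the 95th percentile of Beta(x + 1, n − x). For x = n the upper limit is 100%.

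Assume 48 of 50 are scored successful and 2 of the 48 were assisted: 48/50 = 96.0% (87.9 to 99.3) becomes 46/50 = 92.0% (82.6 to 97.2).

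Assume instead that every unassisted subject succeeds:

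| h | n = 100, h not successful | n = 50, h not successful |
|---|---|---|
| 0 | 100% (97.0 to 100) | 100% (94.2 to 100) |
| 2 | 98.0% (93.8 to 99.6) | 96.0% (87.9 to 99.3) |
| 5 | 95.0% (89.8 to 98.0) | 90.0% (80.1 to 96.0) |
| 10 | 90.0% (83.6 to 94.5) | 80.0% (68.4 to 88.7) |

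Scored as successes, the h subjects leave every row at the h = 0 values.

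**Step 4: does the exclusion rule protect the estimate?** With h = 5 excluded, the result is 95/95 = 100% (96.9 to 100) or 45/45 = 100% (93.6 to 100). The point estimate stays at 100% and the lower limit barely moves, so exclusion does not show the failures either.

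**The case against.** The strongest reply is that the criterion is not just an empty container. Both documents require that the subject did the self-injecting, and the CRF question asks exactly that. An evaluator who saw hands-on help can answer no, or treat the injection as not performed by the subject. A reader might infer that a physically helped subject counts as a success by rule, or that the plan makes no allowance for anyone else's involvement. The documents support neither: takeovers are handled explicitly, and partial physical help is indeterminate.

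Second, staff are assigned to observe and evaluate, and the Week 8 procedures contain no training step. Coaching is therefore not a planned activity. That is true, but it is not excluded either, and the rule gives no instruction if it happens.

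Third, the CRF, its completion guidelines, the Data Cleaning Plan and the device instructions are not available here and may define assistance. This stands as a limit on certainty. It does not remove the need for a primary-endpoint rule in the Protocol and SAP, particularly with up to 80 sites.

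Fourth, nothing shows that staff will prompt, that the evaluators are the trainers, or that a prompted subject would otherwise have failed. The study is descriptive, with no threshold to cross. All of this stands: the frequency and the true bias are unknown, and no decision in the plan is shown to change.

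Fifth, counting any help as failure would let a word of reassurance fail a subject, and would be incoherent if a complete takeover still left the denominator. Both objections are right, and the fix has to meet them.

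**Conclusion.** The gap is real and should be closed. Verbal prompting counts as success under the written rule, partial physical help is left to undefined site judgement, and a takeover is dropped (for one of two 1mL injections the SAP is ambiguous). Against an objective of ability 8 weeks after training, these can raise the percentage and cannot lower it, by up to 1 point per subject at n = 100 and 2 points at n = 50.

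The total size rests on the assumed number of helped subjects, for which the documents give no figure, and on treating inability without help as failure. The documents do not support saying that assistance is common, that the reported percentage will be wrong by a given amount, or that physical help always scores as success.

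**What to change.** 1. In Protocol 4.1.1 and SAP 11.1, state that during the assessed Week 8 injection staff give no instruction or physical help except to prevent harm. The subject may consult the device instructions.
2. Add one yes/no item per injection to the existing self-injection CRF page, recording substantive verbal or physical help. Define substantive so that reassurance alone does not count.
3. Report the Week 8 percentage and its exact 90% CI two ways: under the current rule, and with injections that were assisted, or taken over because the subject could not complete them, counted as not successful.
4. Amend the exclusion sentence in SAP 11.1 so that takeovers and assisted injections are handled consistently. For the 1mL cohort, say what happens when one of the two injections is taken over.
5. For Baseline, show successes with and without help.

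The cost is one CRF item, a few sentences, and possibly a lower success percentage. SAP 3.5 and 5.3 describe recruitment and COVID-19 data collection in the past tense, so some or all visits may already be complete. For those visits the new item cannot be filled in, and what remains is the takeover sensitivity analysis and a stated limitation that prompting was not recorded.
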